8.19 Conventions of ECG Data

All available non-missing values of ECG parameters should be used in the listings, summarizations, and analyses. However, if QTcF is missing and RR in seconds is available, then QTcF will be calculated as

$$QTcF = \frac{QT}{RR^{1/3}}$$

If both QTcF and RR in seconds are missing, then QTcF will be calculated as

$$QTcF = \frac{QT}{(60/HEART\ RATE)^{1/3}}$$

8.20 Percent Compliance Calculation

Percent compliance for the double-blind study medication during the double-blind treatment period is defined for each subject as the number of tablets and injections taken, divided by the number of tablets that should have been taken.

For BMS-986142, the number of tablets that should have been taken is calculated as 1 + the number of days from the first double-blind treatment period dose recorded in the “Record of Study Medication” to the last double-blind treatment dose, times the prescribed daily dose (i.e. 2 tablets per day, one from each bottle). The number of tablets taken is the total number of tablets recorded (sum of bottle 1 and bottle 2) as taken based on the CRF, summed over the days counted when calculating the number of tablets that should have been taken, including the day of the last double-blind treatment dose.

For Lulizumab, the same calculation will be used. The number of injections that should have been administered is calculated as 1 + the number of days from the first double-blind treatment period dose recorded in the “Record of Study Medication” to the last double-blind treatment dose divided by 7. The number of injections administered is the total number of injections recorded as administered based on the CRF, summed over the days counted when calculating the number of injections that should have been administered, including the day of the last double-blind treatment dose.

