4.5 Selection and Timing of Dose for Each Subject

All drug dosing should occur after all study-related assessments, including blood draws, are completed. Refer to [Section 5.3](#) for additional information on the order of procedures.

After randomization, study drug will be dispensed according to the assignment by the IVRS/IWRS system. Study drugs are blinded and will be supplied in bottles for BMS-986142 and its matching placebo for home administration. Doses of lulizumab or matching placebo are to be administered subcutaneously in the clinic or by a health care professional (eg, visiting nurse) in the home if approved by local IRB/EC and the investigator. Doses of BMS-986142 at 350 mg or matching placebo are to be administered orally q24h (one time/day) with water and may be taken with or without food. Three tablets, one tablet from Bottle A and two tablets from Bottle B, will be taken all at the same time, once/day every day. Subjects should be instructed to bring their oral study drug (BMS-986142 or placebo) to be taken at the investigational site at every scheduled visit (eg, weekly if home visits are not performed) to avoid confusion about the timing of dose administration, given the frequency of PK assessments and study procedures during the study. On Day 1 and at Weeks 2, 4, 6, 8, and 10, study drug will be administered in the morning at the study site and after blood samples have been collected and questionnaires have been completed. For subjects who are on a stable dose of HCQ, subjects must also bring their HCQ dose to the site on Day 1, Day 8, Week 2 (Day 15), Week 4 (Day 29) and Week 12 (Day 85) of the study as well as the two follow up visits at Week 15 (Day 106) and Week 18

(Day 127), as the HCQ dose will be administered at the same time as the study drugs in the morning at the study site to enable pre-dose PK samples to be taken. Two post-dose PK samples (2 and 4 hours after dosing) for HCQ and study drugs will also be collected at the Day 8 visit. However, at other visits, drug should be taken at approximately the same time each day.

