For BMS-986142 and matching placebo, each subject will be dispensed a set of two (2) bottles every two weeks during treatment. Bottle A contains 17 tablets and Bottle B contains 34 tablets of blinded study drug. The 3 additional tablets in Bottle A and the additional 6 tablets in Bottle B allow for a +/- 3 day window between each visit in the double-blind phase of the study. All study drug bottles (empty or full) that were dispensed to the subject must be brought back to the study site by the subject at Weeks 1, 2, 4, 6, 8, 10, and 12 during the double-blind period for drug reconciliation/compliance assessments.

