7.5.1 Primary efficacy analysis

The EULAR Sjögren's Syndrome Disease Activity Index (ESSDAI) is a systemic disease activity index that was designed to measure disease activity in subjects with pSS (see Protocol Appendix 3).³³ The ESSDAI parameters are assessed by the investigators and the results from each assessment are recorded in site source records as well as entered into the corresponding eCRF. The ESSDAI total score will be calculated as described in [section 8.6](#)

The primary efficacy endpoint is change from baseline ESSDAI score at Week 12.

The mixed effects model with repeated measures (MMRM) will be used to model the change from baseline in ESSDAI score over time for all treatment arms. Details of the model are presented in [section 7.1.5.1](#).

The least square means of the differences of Week 12 change in ESSDAI from baseline between each active treatment and the placebo will be estimated and their corresponding two-sided 95% confidence intervals will be provided.

The Hochberg's step-up procedure will be used to adjust the multiplicity due to the comparison of two active treatments (lulizumab or BMS-986142) to the placebo arm. The corresponding adjusted p-values for the Hochberg procedure will be provided.

The model assumption assessment will be performed following the methodology described in [section 7.1.5.2](#).

In addition, the same model will be used to provide estimates for the changes in ESSDAI score at each time point of assessment as per protocol.

In case that more than 10% of subjects in any treatment group have a relevant protocol deviation, leading to exclusion of efficacy data, then this analysis will be repeated excluding efficacy data from subjects with relevant protocol deviations, as described in [APPENDIX 1](#).

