APPENDIX 1 RELEVANT PROTOCOL DEVIATIONS

Number	Relevant Protocol Deviation Criteria	Exclusion Level
1	Randomized subjects who do not have moderate to severe primary Sjögren's syndrome, defined as Sjögren's syndrome in the absence of another autoimmune disease or rheumatologic condition) based on the 2015 ACR-EULAR Classification Criteria.	Complete exclusion
2	Randomized subjects without ESSDAI \geq 5, including disease activity (any score $>$ 0) in at least one of the following domains: Glandular, Articular, Hematological, Biological, Lymphadenopathy.	Complete exclusion
3	Randomized subjects without Positive anti-SS-A/Ro or anti-SS-B/La autoantibody.	Complete exclusion
4	Randomized subjects who received more than 10mg/day of prednisone (or prednisone equivalent) for at least 14 days prior to Day 1 (randomization).	Complete exclusion
5	Randomized subjects who did not receive at least 4 consecutive doses of Lulizumab or matching placebo.	Partial exclusion (Efficacy data after the 21th day of the interruption will be excluded)
6	Randomized subjects who did not receive BMS-986142 or matching placebo for at least 14 consecutive days.	Partial exclusion (Efficacy data after the 14th day of the interruption will be excluded)
7	Randomized subjects to placebo receiving active medication dose of Lulizumab for at least 4 doses and BMS-986142 for at least 14 doses.	Partial exclusion (Efficacy data from the first dose date of active medication will be excluded)
8	Randomized subjects receiving initiating or increasing the baseline dose (if already in such a medication) in any of the protocol specified list of restricted and prohibited treatments during double-blind treatment period.	Partial exclusion (Efficacy data from the first dose date of restricted or protocol medication will be excluded)
9	Randomized subjects less than 80% or more than 120% compliant with any of the double-blind treatment regimens.	Complete exclusion

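### SAP 8.20 expects 2 tablets a day where the protocol has subjects take 3, so full adherence scores 150% and the per-protocol rule removes everyone above 80% adherence

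*SAP*

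**What the plan says.** SAP 8.20 defines the expected tablet count for BMS-986142 or its placebo as the number of days from first to last dose, plus one, "times the prescribed daily dose (i.e. 2 tablets per day, one from each bottle". For the numerator, "The number of tablets taken is the total number of tablets recorded (sum of bottle 1 and bottle 2") as taken on the CRF.

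Protocol 4.5 gives a different daily count: "Three tablets, one tablet from Bottle A and two tablets from Bottle B, will be taken all at the same time, once/day every day". It also describes the two-weekly supply: "Bottle A contains 17 tablets and Bottle B contains 34 tablets of blinded study drug". Of these, 3 tablets in Bottle A and 6 in Bottle B are spares for a visit window of plus or minus 3 days.

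The compliance percentage feeds SAP Appendix 1, criterion 9: "Randomized subjects less than 80% or more than 120% compliant with any of the double-blind treatment regimens". The exclusion level for that criterion is complete exclusion. Two places say when the exclusions are used. SAP 7.5.1 requires the primary analysis to be repeated without the excluded data: "In case that more than 10% of subjects in any treatment group have a relevant protocol deviation" that leads to exclusion of efficacy data. SAP 7.2 makes a per-protocol analysis optional once at least 10% of all subjects in the efficacy population have relevant deviations. It also says that such subjects stay in every defined analysis population.

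**The concern.** The numerator counts tablets as the protocol dispenses them, three a day. The denominator counts two a day. A subject who does exactly what the protocol asks is therefore scored well above 100%, and above the 120% limit.

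The design is double-dummy, so subjects in all three arms take tablets and the error does not fall on one arm alone. Two things are at stake. The summary of relevant deviations would list adherent subjects as non-compliant. The per-protocol repeat of the primary endpoint would discard adherent subjects and keep those who missed a fifth or more of their tablets, which is the reverse of what a per-protocol analysis is for.

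**Working it through.** **Inputs**

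- SAP 8.20: 2 tablets expected per day; tablets from both bottles are counted as taken; days = 1 + (last dose date − first dose date).
- Protocol 4.5: 3 tablets per day; 17 and 34 tablets per two weeks, with 3 and 6 spare; 350 mg once daily or matching placebo.
- Protocol 4.1: tablet strengths 50 mg and 150 mg.
- Protocol 3.1: treatment period of 84 days.
- SAP Appendix 1, criterion 9: accepted band 80% to 120%.

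**Step 1. Can the SAP's figure of 2 per day be reproduced from the protocol?** It cannot.

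- Bottle A: (17 − 3)/14 = 1 per day. Bottle B: (34 − 6)/14 = 2 per day. Total 3.
- Strengths: two tablets give 100, 200 or 300 mg, never the 350 mg stated in Protocol 4.5 and in SAP 6.2. One 50 mg plus two 150 mg tablets give 350 mg. (Protocol 4.5 does not say which strength is in which bottle; the bottle counts settle the number of tablets without it.)

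**Step 2. Score for perfect adherence over 84 days.**

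- Taken: 3 × 84 = 252.
- Expected under SAP 8.20: 2 × (1 + 83) = 168.
- Score: 252/168 = 150%.

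**Step 3. Other readings of SAP 8.20.** The section is loosely worded, and its opening sentence puts tablets and injections together over tablets alone. With 12 injections in a full course:

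| Reading | Score |
|---|---|
| Denominator as 1 + (83 × 2) = 167 | 252/167 = 150.9% |
| 85 dosing days | 255/170 = 150.0% |
| Tablets plus injections over tablets | 264/168 = 157.1% |
| Tablets plus injections in both terms | 264/180 = 146.7% |

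All exceed 120%.

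**Step 4. What the 80% to 120% band means in true adherence.** The score is 3/2 = 1.5 times true adherence, so the band runs from 0.80/1.5 = 53.3% to 1.20/1.5 = 80.0%.

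| True adherence | SAP score | Criterion 9 |
|---|---|---|
| 50% | 75% | excluded |
| 60% | 90% | kept |
| 70% | 105% | kept |
| 80% | 120% | kept |
| 81% | 121.5% | excluded |
| 90% | 135% | excluded |
| 100% | 150% | excluded |

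**Step 5. The trigger.** With 25 subjects per arm, more than 10% of a group is reached by 3 subjects (3/25 = 12%; 2/25 = 8%). With 75 in total, 10% is reached by 8 subjects (7.5 rounded up). Since everyone above 80% adherence counts as a deviator, both thresholds are met almost automatically if adherence is good.

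**Step 6. Injections.** The last of 12 weekly injections is 77 days after the first. The formula gives 12/(1 + 77/7) = 100%, or 12/((1 + 77)/7) = 107.7% if the division covers the whole expression. Neither leaves the band, so the problem lies in the tablet count.

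**The case against.** The strongest case on the other side concerns reach.

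- **The primary result is untouched.** Efficacy is analysed on MITT, and SAP 7.2 keeps subjects with deviations in every analysis population. The treatment compliance summary in SAP 7.4.3 counts missed injections and doses and does not use this formula. This stands: the damage is confined to the compliance percentages, the deviation summary and the per-protocol analysis.
- **The per-protocol analysis may not be run.** It is optional under SAP 7.2 and mandatory only under SAP 7.5.1. This stands as a point about the two rules, but inflated scores would meet both thresholds.
- **The band is not the whole rule.** The denominator stops at the last dose, so 53.3% to 80.0% is adherence while on treatment. Retention also depends on injection compliance and the other eight criteria. A subject at exactly 80% scores 120% and stays in. These refinements are correct and do not change the direction of the error.
- **Someone would notice.** The governing words refer to the prescribed daily dose, the figure of 2 is a parenthetical gloss, and near-universal scores of about 150% would be conspicuous when deviations are identified before lock. That lowers the practical risk. It does not make the written rule right, and a correction made only in programming would be an undocumented departure from the SAP.

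**Conclusion.** The concern holds. SAP 8.20 and Protocol 4.5 contradict each other on the daily tablet count, and the protocol's bottle counts agree with three. As written, full adherence scores 150% (146.7% to 157.1% across the readings tried), and criterion 9 excludes from the per-protocol analysis every subject whose true tablet adherence is above 80%, in all three arms.

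How few subjects would remain depends on actual adherence, which the documents do not give; if adherence is good, the per-protocol set is close to empty. The conclusion assumes that the CRF records tablets as actually taken and that the 2-per-day gloss is programmed literally. It takes no position on the dose. Because the MITT analysis is unaffected, this should be corrected but does not threaten the primary result.

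**What to change.** Reconcile SAP 8.20 with Protocol 4.5 so that a subject who takes exactly the prescribed tablets scores 100%. The denominator should be days on treatment multiplied by the daily tablet count in the reconciled dosing instruction, cited by section so that the two cannot drift apart. On the present Protocol 4.5 text this gives 252/252 = 100%, and the 80% to 120% band again means 80% to 120% true adherence.

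In the same edit:

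- Rewrite the opening sentence of SAP 8.20 so that tablet and injection compliance are two separate percentages, each with its own denominator, and make clear what is divided by 7 in the injection formula.
- Apply criterion 9 to the corrected values.
- Align the per-protocol triggers in SAP 7.2 and 7.5.1.

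The cost is a short SAP correction and a programming change. Both should be done before deviations are identified, and so before database lock and unblinding. No data collection changes.

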BMS-931699 (lulizumab) is an anti-human cluster of differentiation (CD)28 receptor antagonist V κ domain antibody (dAb), formatted with 40 kDa branched polyethylene glycol (PEG). It will be administered subcutaneously (SC) at a dose of 12.5 mg weekly in a double-blind fashion for 12 weeks.

BMS-986142 is a reversible Bruton's tyrosine kinase (BTK) inhibitor that will be administered orally at a dose of 350 mg daily in a double-blind fashion for 12 weeks.

Study Phase: II

Research Hypothesis: Treatment with BMS-931699 (lulizumab) or BMS-986142 for 12 weeks is more effective than placebo in decreasing the ESSDAI score in subjects with moderate to severe primary Sjögren's syndrome (pSS).

Objectives:

Primary: To evaluate the efficacy of treatment with either lulizumab or BMS-986142 versus placebo in subjects with moderate to severe primary Sjögren's syndrome as measured by the change from baseline in ESSDAI at Week 12 between active treatment arms (lulizumab or BMS-986142, respectively) and the placebo arm.

Secondary:

To assess the:

- Change from baseline in ESSPRI score at Week 12
- Proportion of subjects with a ≥ 3 point improvement from baseline in ESSDAI at Week 12
- Proportion of subjects with a ≥ 1 point improvement from baseline in ESSPRI at Week 12
- Proportion of subjects with both ≥ 3 point improvement in ESSDAI and ≥ 1 point improvement in ESSPRI from baseline at Week 12
- Change from baseline in ESSDAI scores at Week 4 and Week 8
- Change from baseline in ESSPRI scores at Week 4 and Week 8
- Change from baseline in ESSPRI components (Dryness, Fatigue, and Pain) at Week 4, 8 and 12
- Change from baseline in unstimulated and stimulated salivary flow rate at Weeks 4, 8, and 12
- Change from baseline in ocular surface staining, Schirmer's test, and tear-break up time test at Weeks 4, 8, and 12
- Safety and tolerability of lulizumab or BMS-986142 in subjects with moderate to severe pSS, as measured by adverse events, laboratory parameters, vital signs, physical exams, and ECGs
- Change from baseline in patient and physician assessments of disease activity:
 - Numeric rating scale (NRS) scores for mouth, eye and vaginal dryness
 - Subject global assessment of disease activity (SubGDA) and physician global assessment of disease activity (phyGDA)
 - PROMIS Fatigue Short Form
 - Short Form-36 acute (SF-36 acute)

- Female Sexual Function Index (FSFI)
- Work participation and activity impairment questionnaire (WPAI)

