	Day 1 (Baseline)	Day 8 (Week 1)	Day 15 (Week 2)	Day 22 ^c (Week 3)	Day 29 (Week 4)	Day 36 ^c (Week 5)	Day 43 (Week 6)	Day 50 ^c (Week 7)	Day 57 (Week 8)	Day 64 ^c (Week 9)	Day 71 (Week 10)	Day 78 ^c (Week 11)	Day 85 (Week 12)	Day 106 (Week 15)		Day 127 (Week 18)
Staining ^e																
Tear Break-up Time Test ^e	X				X					X			X			See Section 5.4.2.1
Unstimulated and Stimulated Salivary Flow	X				X					X			X			Subjects should refrain from eating/drinking for 90 min prior to tests. Specimens should be retained in separate containers for biomarker analysis. See Section 5.4.2.2
Sicca symptoms Numeric Rating Scales (NRS)	X		X		X		X		X		X		X		X	Oral, ocular & vaginal dryness scales. See Section 5.7
phyGDA	X		X		X		X		X		X		X		X	See Section 5.7
subGDA	X		X		X		X		X		X		X		X	See Section 5.7
PROMIS Fatigue SF	X				X					X			X		X	See Section 5.7
SF-36 (acute)	X				X					X			X		X	See Section 5.7
Female Sexual Function Index (FSFI)	X				X					X			X		X	See Section 5.7
Work Participation	X				X					X			X		X	See Section 5.7

Table 5.1-2: Short-term Procedural Outline (IM128035)

Procedure	During Treatment ^a												End of Trt ^{a,b}	FU #1 ^a	FU #2 ^a	Notes
	Day 1 (Baseline)	Day 8 (Week 1)	Day 15 (Week 2)	Day 22 ^c (Week 3)	Day 29 (Week 4)	Day 36 ^c (Week 5)	Day 43 (Week 6)	Day 50 ^c (Week 7)	Day 57 (Week 8)	Day 64 ^c (Week 9)	Day 71 (Week 10)	Day 78 ^c (Week 11)	Day 85 (Week 12)	Day 106 (Week 15)	Day 127 (Week 18)	
and Activity Impairment Questionnaire (WPAI)																
Study Drug																
Randomize through IVRS/IWRS system	X															
Dispense supplies of BMS-986142 or matched placebo for home administration	X		X		X		X		X		X					Daily dosing of BMS-986142 or matched placebo at home or in the clinic. Subject should bring dose to the clinic to be administered at the site on study visit days.
Dosing of subcutaneous lulizumab or matched placebo	X	X	X	X	X	X	X	X	X	X	X	X				Subjects should be observed in the clinic for 2 hours after dosing on Day 1, then 1 hour after dosing for subsequent doses.
Reconciliation of oral Study Medication (BMS-986142 or matched placebo)		X	X		X		X		X		X		X			

- a Visit window of ± 3 days
- b All procedures scheduled for the End of Week 12/End of treatment visit should be performed at the time of actual discontinuation/end of treatment.
- c May be a home visit conducted by visiting health care professional if approved by IRB and investigator. If visit is a home visit, the subject's signs and symptoms will be assessed.

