7.4.3 Treatment Compliance

The CRF for this study will capture information on injections of the Lulizumab or matching placebo and doses of BMS-986142 or matching placebo.

The number of subjects with missed injections or doses (excluding missed injections or doses due to premature discontinuation from the study) will be summarized by number of missed injections or doses based on the As-treated analysis population for the ST period by treatment groups. The summary will be produced separately for missed injections and missed doses. A corresponding listing for all subjects who skip either any injection or dose will be produced.

[REDACTED]

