 - ◆ If the derived date is prior to the surrogate date and the surrogate date is not consistent with the partial data provided for the onset date then set the derived onset date to be the latest possible date based on the partial onset date information provided. If only a year is provided, set the derived date to December 31st of that year. If a year and month is provided, set the derived date to the last day of that month.
 - If all three dates used to determine the surrogate date are missing, then based on the information provided, set the derived date to the earliest possible date. If only a year is provided, set the derived date to January first of that year. If a year and month is provided, set the derived date to the first day of that month.

A drug treatment file will be created, containing any starting and stopping dose as well as intermediate dose changes within each study period, with dates and times as recorded on the CRF. In this context,

- the date of the first dose of study medication is defined as the earliest start date with number of tablets > 0 or injections > 0 reported on the study medication page.
- the date of the last dose of study medication is defined as the latest start or stop date with number of tablets > 0 or injections > 0 reported on the study medication page.

- if a dosing time is missing for a starting dose of study drug in a study period or a dose change, then it is defaulted to 9:00.
- if there's a gap in the dosing information, then the dosing time corresponding to the start date of the gap, is defaulted to 00:00.

If a dosing time is missing for a last stop dosing date for the study drug in a study period, then it is defaulted to 23:59.

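### SAP 8.20 ends the expected-injection count at the last dose, so injections missed at the end of treatment can drop out of the compliance denominator and pass the 80% cut

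*SAP*

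**What the plan says.** The protocol synopsis gives lulizumab at "12.5 mg weekly in a double-blind fashion for 12 weeks". In Protocol Table 5.1-2 the row "Dosing of subcutaneous lulizumab or matched placebo" carries 12 marks, from Day 1 to Day 78, with none at Day 85. Every subject receives both injections and tablets, active or placebo.

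SAP 8.20 takes expected injections as 1 plus the number of days from the first dose "to the last double-blind treatment dose divided by 7". For the numerator: "The number of injections administered is the total number of injections recorded as administered based on the CRF", summed up to the day of the last dose. The injection paragraph says that it follows the tablet calculation. It does not say which product's last dose closes the interval, and the formula has no brackets.

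Appendix 1, criterion 9, makes the following a complete exclusion: "Randomized subjects less than 80% or more than 120% compliant with any of the double-blind treatment regimens". Criterion 5 is a partial exclusion: "Randomized subjects who did not receive at least 4 consecutive doses of Lulizumab or matching placebo". SAP 7.2 allows a per-protocol analysis if at least 10% of all subjects deviate. SAP 7.5.1 repeats the primary analysis without the excluded data if more than 10% of any arm deviate. SAP 7.4.3 summarises missed doses "excluding missed injections or doses due to premature discontinuation from the study".

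**The concern.** A compliance percentage should tell the reader what share of the planned injections a subject received while on treatment. A denominator that ends at the last dose taken does not do this for doses missed at the end. Two subjects who each miss three of 12 injections can fall on opposite sides of the 80% cut, depending only on when the misses occurred. The subject who is kept is the one with no injection in the weeks just before the Week 12 ESSDAI.

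At stake are the compliance figures, the membership of the per-protocol set, and the count of deviators that decides whether the per-protocol repeat is run. With about 25 subjects per arm, three deviators (3/25 = 12%) exceed the 10% trigger in SAP 7.5.1, so a few misclassified subjects could matter. Deviators must also be identified before unblinding (SAP 7.2), so the rule has to be unambiguous by then.

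**Working it through.** **Inputs.** Twelve weekly injections on Days 1, 8, …, 78 (Protocol Table 5.1-2). Limits of 80% and 120% (Appendix 1, criterion 9). The last tablet day is not settled: the 84-day treatment period in Protocol 3.1 suggests Day 84, while the predose BMS-986142 sample at Day 85 in Protocol Table 5.5-1 suggests Day 85. Both are shown. Visits are assumed to fall on target days and the first injection is given.

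**Reproducing the plan.** With the last injection on Day 78, the denominator is 1 + 77/7 = 12, the planned number. For any subject who receives the Day 78 injection on schedule, this reading returns exactly n/12.

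**Reading A: last dose = last injection, 1 + days/7.**
- Three missed in mid-course: 9/(1 + 77/7) = 9/12 = 75%, excluded.
- Days 64, 71 and 78 missed while tablets continue: the last injection is on Day 57, so 9/(1 + 56/7) = 9/9 = 100%, kept.
- Criterion 5 does not catch the second subject, because its threshold is four consecutive doses and only three were missed.
- The Week 12 value is also retained: Day 57 + 28 = Day 85, within the 28-day limit for efficacy data in SAP 8.3.

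The patterns with exactly three misses number C(11,3) = 165. Those that include the final dose number C(10,2) = 45, and all 45 score at least 80%:
- 36 score 9/11 = 81.8%
- 8 score 9/10 = 90%
- 1 scores 9/9 = 100%

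**Reading B: last dose = last dose of either product.** This follows the definition in SAP 8.4: "latest start or stop date with number of tablets > 0 or injections > 0 reported on the study medication page".

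| Grouping | Last tablet | Denominator | 12 given | 10 given (true 83.3%) | 9 given (true 75%) |
|---|---|---|---|---|---|
| 1 + days/7 | Day 84 | 1 + 83/7 = 12.86 | 93.3% | 77.8%, excluded | 70.0%, excluded |
| 1 + days/7 | Day 85 | 1 + 84/7 = 13 | 92.3% | 76.9%, excluded | 69.2%, excluded |
| (1 + days)/7 | Day 84 | 84/7 = 12.00 | 100% | 83.3%, kept | 75.0%, excluded |
| (1 + days)/7 | Day 85 | 85/7 = 12.14 | 98.8% | 82.4%, kept | 74.1%, excluded |

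**Reading A with (1 + days)/7.** The Day 57 subject scores 9/(57/7) = 110.5% and is still kept. A full course scores 12/(78/7) = 107.7%.

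The end-of-course effect under reading A therefore survives either grouping. The exclusion of subjects at 83.3% needs both reading B and the 1 + days/7 grouping.

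**The case against.** The case for leaving SAP 8.20 as it stands has several parts.

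- **Reading B is the weaker one.** SAP 8.20 treats each product in its own paragraph, SAP 8.3 uses last-dose dates by product, and the either-product definition in SAP 8.4 is limited to assigning doses to adverse events and laboratory data. This stands. A reader might infer that the plan will remove subjects at 83% compliance, but the documents do not establish that, because it also depends on an unstated grouping.
- **Most subjects are scored correctly.** A reader might infer that no reading ever returns the true share of scheduled injections. That is not so: reading A is exact for anyone who receives the Day 78 injection on schedule.
- **The pattern count is not a rate.** 45 of 165 is 27% of patterns, not of subjects. The documents give no frequency of missed injections, and 36 of the 45 score only just above the cut.
- **Early stoppers are treated consistently.** For a subject who stops both products, counting only to the last dose agrees with SAP 7.4.3. The defect is confined to subjects who miss late injections while still on study treatment.
- **Keeping the Day 57 subject fits other SAP rules.** The 28-day window and the four-dose threshold both admit this subject, and in two of the three arms the injection is saline (Protocol 4.1). This lessens the consequence. It does not explain why the same three misses in mid-course lead to complete exclusion.
- **The misses stay visible.** SAP 7.4.3 lists every subject who skips an injection. That helps a reader of the report, but criterion 9 still works from the percentage.

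**Conclusion.** The point holds and is minor. On its natural reading, SAP 8.20 gives 100% to a subject who stays on study treatment and misses the last three of 12 injections, and 75% to one who misses three in mid-course. Only the second is excluded. The missing brackets and the unnamed last dose add a further ambiguity, which could take 10 of 12 injections from 83.3% to about 77–78%, but only under one combination of readings.

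A reader might infer that the main efficacy result is at risk. It is not: the primary analysis uses the MITT population, and SAP 7.2 removes no deviator from any defined population. Only the compliance figures, the deviation count and the conditional per-protocol analysis can change. The figures assume visits on target days and a first injection given. How many subjects would be affected cannot be estimated from the documents.

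**What to change.** In SAP 8.20, define expected injections as the number of scheduled weekly injection visits from Day 1 to Day 78 (maximum 12) that fall on or before the date the subject discontinued study treatment. Compute compliance as injections received divided by that number. Counting by visit makes brackets unnecessary, removes any effect of the ±3-day window, and keeps the SAP 7.4.3 treatment of subjects who stop early.

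For tablets, end the expected count at the end of the treatment period or the discontinuation date, not at the last tablet taken. The documents must first be reconciled on whether the last tablet day is Day 84 or Day 85. The same rewrite can settle the number of tablets per day, which is two in SAP 8.20 and three in Protocol 4.5.

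The cost is a few sentences of SAP text and one derivation, from the visit schedule and from dosing and discontinuation data already collected. The downside is that subjects who miss doses at the end will show lower compliance, and some will newly fall under criterion 9. The change should be made before deviators are identified and the blind is broken.
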